### 5.3.3 Drug-Drug Interactions

The potential of pharmacokinetic drug-drug interaction was tested *in vitro*. Fruquintinib was not a substrate of efflux transporters. Fruquintinib showed dose-dependent inhibition on P-gp and BCRP. Based on the data for digoxin transport (mediated by P-gp) and estrone-3-sulfate transport (mediated by BCRP), the IC50 on P-gp and BCRP was estimated to be 4.60 and 1.29 μM, respectively.

According to the present metabolism data, enzymes CYP3A4/5 play an important role in the metabolism of fruquintinib. Fruquintinib had no marked inhibitory effects on CYPs 1A2, 2B6, 2C8, 2C9, 2C19, 2D6, and 3A4/5 (IC50 >10 μM) and no induction of CYP1A2, [REDACTED] and CYP3A4 at the tested concentration of 10 μM. No marked time-dependent inhibition was observed for CYPs 1A2, 2B6, 2C8, 2C9, 2C19, 2D6, and 3A4/5.

Substrates of P-gp and BCRP, and inducers and inhibitors of CYP3A4/5 should not be administered concomitantly with fruquintinib, unless investigators consider it necessary. In this case, efficacy reduction and toxicity increases resulting from the interaction should be closely monitored. Examples of the medicines to avoid are listed in [Appendix F](#).

## 6 STUDY VISITS, ASSESSMENTS, AND METHODS

### 6.1 Screening and Pre-treatment Assessments

Written informed consent for participation in the study must be obtained before performing any study-specific screening tests or procedures. Medical history and demographic information, including clinically significant diseases within the previous 5 years, oncology history (including cancer name, primary diagnosis date, stage of diagnosis, prior anti-cancer therapies, and procedures) should be recorded in CRF. Informed consent forms for patients who are not subsequently enrolled will be maintained at the study site. All screening evaluations must be completed and reviewed by the investigator and the clinical monitor to confirm that patients meet all eligibility criteria before the first administration of fruquintinib.

Please see the Study Flowchart provided in [Appendix A](#) for the schedule of screening and pre-treatment assessments. Screening and pre-treatment tests will be performed within 28 days of the first dose of study drug, unless otherwise specified. Results of standard of care tests performed prior to obtaining informed consent and within 28 days prior to study entry may be used (except hematology, coagulation tests, clinical chemistry, or urinalysis results).

### 6.2 Assessments During Treatment Phase

All visits must occur within  $\pm 3$  days ( $\pm 1$  day during cycle 1) from the scheduled date, unless otherwise noted (see [Appendix A](#)). All assessments will be performed on the day of the specified visit unless a time window is specified. Please see the Study Flowchart provided in [Appendix A](#) for the schedule of treatment period assessments.

If scheduled study assessments cannot be obtained because of a holiday, assessments during Cycle 1 should be done either prior to or immediately after the schedule interruption, regardless of the proximity to the next scheduled visits. If assessments cannot be obtained due to a holiday for any other cycle, these assessments should be obtained at the soonest following date, unless the soonest following date is within 7 days of other, regularly scheduled study assessments.

If during the DLT assessment window, 2 or more patients in a single cohort experience the same study drug-related Grade 3 toxicity that does not otherwise qualify as a DLT, the patients subsequently enrolled to this dose level and to the subsequent dose level will undergo increased monitoring during Cycle 1, as clinically indicated. Note: DLTs will not be collected during the Dose Expansion Phase.

### 6.3 Safety Assessments

#### 6.3.1 Vital Signs Assessment

Vital signs will include measurements of body temperature, heart rate, respiratory rate, and systolic and diastolic blood pressure while the patient is in a seated position. The patient should be seated for approximately 5 minutes before the measurement of the blood pressure. For patients with a baseline history of hypertension, or those who develop hypertension during the study, blood pressure should be monitored daily by the patient at home, at

3 hours ( $\pm 2$  hours) after the daily doses of anti-hypertensive medication, and the results recorded in a blood pressure diary. Patients monitoring their blood pressure should bring their diary to each study visit.

### **6.3.2 Physical Examination**

A complete physical examination at screening should include the evaluation of head, eye, ear, nose, and throat; and cardiovascular, dermatological, musculoskeletal, respiratory, gastrointestinal, and neurological systems.

At subsequent visits, a limited physical examination will be performed to assess changes from baseline abnormalities, any new abnormalities, and to evaluate patient-reported symptoms. New or worsened abnormalities should be recorded as AEs if appropriate. In order to assess changes from baseline and screen for new abnormalities, the limited physical examination should assess for new or changed skin lesions, enlarged lymph nodes, and palpable masses. Patient-reported symptoms should be directed to address the symptoms.

Body height will be measured only at screening.

### **6.3.3 Laboratory Tests**

Samples for hematology, serum chemistry, urinalysis pregnancy, thyroid function, and specific tumor marker testing will be analyzed at the study site's local laboratory. Laboratory assessments will include the following:

Hematology (complete blood count [CBC], including red blood cell [RBC] count, hemoglobin, hematocrit, reticulocyte count, white blood cell [WBC] count with differential [neutrophils, eosinophils, lymphocytes, monocytes, basophils, and other cells], and platelet count; INR and aPTT);

Serum chemistry (blood urea nitrogen [BUN], creatinine and creatinine clearance, sodium, potassium, chloride, bicarbonate, calcium, magnesium, phosphorus, glucose, triglycerides, total bilirubin, total cholesterol, ALT, AST, alkaline phosphatase (ALP), lactate dehydrogenase [LDH], uric acid, total protein and albumin);

Serum pregnancy test at screening and at the Treatment Completion Visit for all women of childbearing potential, including those who have had a tubal ligation;

Urine pregnancy test at each day 1 visit, starting at Cycle 2 Day 1, for all women of childbearing potential, including those who have had tubal ligation;

Urinalysis (pH, glucose, protein, and blood);

Thyroid function (thyroid stimulating hormone [TSH], free T3, and free T4); and

Specific tumor markers (tumor markers to be collected will be addressed in Section 6.4)

The normal value range of laboratory examination indicators at the study site's local laboratory will be collected prior to the study.

### **6.3.4 Cardiac Monitoring**

Left ventricular ejection fraction (LVEF) assessed via echocardiogram and 12-lead ECGs

are required to be performed as scheduled; ECG shall be performed pre-dose and at 3 hours ( $\pm$  15 minutes) post fruquintinib dose on Days 1 and 15 in Cycle 1. ECG will be conducted on Day 1 of each cycle from Cycle 2 and onward. QTcF interval should be calculated and be closely monitored. See [Appendix A](#). MUGAs are permitted if echocardiograms cannot be performed.

Test results will be reviewed by the investigator to determine patient eligibility at screening. Additional tests and other cardiac monitoring should be performed as clinically indicated during the study.

## 6.4 Efficacy Assessments

### Tumor Assessment

All measurable and evaluable lesions should be assessed and documented at screening and re-assessed at each subsequent tumor evaluation (see [Appendix A](#)). Assessments should include computed tomography (CT) scans with oral or IV contrast (unless contraindicated) of the chest, abdomen, and pelvis. MRI scans are allowed if CT contrast is contraindicated. Other methods of assessment should be utilized as clinically indicated.

**Tumor assessments for dose escalation cohorts, Dose Expansion Cohort C, Dose Expansion Cohort D, and Dose Expansion Cohort E** are scheduled at Screening and every 8 weeks ( $\pm$ 1 week) thereafter, ie, C3D1, C5D1, C7D1, etc. (odd-numbered cycles).

**Tumor assessments for Dose Expansion Cohort A and Dose Expansion Cohort B** are scheduled at Screening, C2D1, C3D1, C4D1, and every 8 weeks ( $\pm$ 1 week) thereafter, ie, C6D1, C8D1, C10D1, etc. (even-numbered cycles).

Subjects who permanently discontinue study drug for reasons other than progression of disease should continue to be followed for efficacy according to the schedule in [Appendix A](#).

All subjects are to have tumor assessments performed at the Treatment Completion visit, unless the subject was discontinued from treatment because of disease progression or the subject had tumor assessments performed within 14 days of the last dose of study drug.

At the investigator's discretion, CT scans may be repeated at any time if progressive disease is suspected.

Disease status will be assessed using RECIST Version 1.1 (see [Appendix C](#)). The same imaging procedure used to define measurable lesions at baseline must be used throughout the study for each patient.

At the investigator's discretion, other methods of assessment of measurable disease as per RECIST may be used. Examples of other assessment methods include tumor markers, such as prostate-specific antigen (PSA) and cancer antigen 125 (CA-125) levels for patients with prostate and ovarian cancer, respectively. However, tumor markers alone cannot be used to assess response. If markers are initially above the upper normal limit, they must normalize for a patient to be considered in complete response.

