**Appendix A Study Schedule of Events**

Date Procedure	Treatment 											Treatment Completion 	Follow-up
	Screening		Cycle 1				Cycle 2-3		Cycle 4 and onwards				
	Day -28 to Day -1	Day -7 to Day -1	Day 1	Day 8 (±1d)	Day 15 (±1d)	Day 22 (±1d)	Day 1 (±3d)	Day 15 (±3d)	Day 1 of each subsequent cycle (±3d)				
Informed consent 	X												
Tumor assessment (Dose Escalation, Expansion Cohorts C, D, E)	X		Screening, then every 8 (±1) weeks thereafter ( eg C3D1, C5D1, C7D1, etc.)								X 		
Tumor assessment (Dose Expansion Cohorts A and B only)	X		Screening, C2D1, C3D1 C4D1, and every 8 (±1) weeks thereafter (eg C6D1, C8D1, C10D1, etc.)								X 		
Medical history, demographics	X												
Concomitant medication 	X	X	X	X	X	X	X	X	X	X	X	X	
ECOG performance status		X	X		X		X	X	X	X	X	X	
Vital signs 		X	X	X	X	X	X	X	X	X	X	X	
Complete physical examination 		X											
Limited physical examination 			X	X	X	X	X	X	X	X	X	X	
Height	X												
Hematology 		X		X	X	X	X	X	X	X	X	X	

Date Procedure	Screening		Treatment 							Treatment Completion 	Follow-up
			Cycle 1				Cycle 2-3		Cycle 4 and onwards		
	Day -28 to Day -1	Day -7 to Day -1	Day 1	Day 8 (±1d)	Day 15 (±1d)	Day 22 (±1d)	Day 1 (±3d)	Day 15 (±3d)	Day 1 of each subsequent cycle (±3d)	30 (±7) days after permanent treatment discontinuation	Every 12 (±2) weeks from Treatment Completion Visit
Coagulation assay (aPTT, INR)		X		X	X	X	X	X	X	X	
Chemistry panel 		X		X	X	X	X	X	X	X	
Urinalysis 		X		X	X	X	X	X	X	X	
Echocardiogram 	X		X (Every 12 weeks ± 1 week after the first dose)							X	
Thyroid function test 	X						X		X	X	
Serum pregnancy tests 		X								X	
Urine pregnancy tests 							X		X		
Specific tumor markers  Dose Escalation, Expansion Cohorts C, D, E)	X		Screening, then every 8 (±1) weeks thereafter: C3D1, C5D1, C7D1, etc								
Specific tumor markers  Dose Expansion Cohorts A and B only)			Screening, C2D1, C3D1 C4D1, and every 8 (±1) weeks thereafter								
12-lead electrocardiogram 		X	X		X		X		X	X	
PK plasma sampling			PK samples are being collected on Days 1, 2, 14, and 15 of Cycle 1 for Expansion Cohorts B, C, D, and E. Refer to Appendix D for								

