Date Procedure	Screening		Treatment 							Treatment Completion 	Follow-up
			Cycle 1				Cycle 2-3		Cycle 4 and onwards		
	Day -28 to Day -1	Day -7 to Day -1	Day 1	Day 8 (±1d)	Day 15 (±1d)	Day 22 (±1d)	Day 1 (±3d)	Day 15 (±3d)	Day 1 of each subsequent cycle (±3d)	30 (±7) days after permanent treatment discontinuation	Every 12 (±2) weeks from Treatment Completion Visit
			specific timepoints								
Adverse event 	X	X	X	X	X	X	X	X	X	X	
Fruquintinib treatment			Once daily, 3 weeks on/ 1 week off								
Survival follow up 											X

Note:

1. A written informed consent form should be obtained prior to any protocol-specific procedure or test. Tests completed within 28 days prior to enrollment can be used for screening and do not need to be repeated (except hematology, coagulation test, clinical chemistry, or urinalysis results).
2. Unless otherwise indicated, the visit window during the treatment period will be ± 3 days (± 1 day during cycle 1).
3. Patients who complete or prematurely discontinue the study need to return to the study site for a follow-up at 30 (±7) days after the decision to discontinue treatment permanently. Ongoing AEs will be followed until the event has resolved to baseline grade, the event is assessed as stable by the investigator, new anti-tumor treatment is initiated, the patient is lost to follow-up, the patient withdraws consent, or when it has been determined that the study treatment or participation is not the cause of the AE.
4. The treatment completion visit tumor assessment can be omitted if treatment ended because of disease progression or the patient had a tumor assessment within 14 days prior to the last dose of study drug.
5. Concomitant medication includes any prescribed or over-the-counter medicines. All medication used by patients within 7 days before screening and 30 days after study treatment completion should be recorded. At each visit, all medication used since the prior visit should be recorded.

6. Vital signs include blood pressure, heart rate, respiratory rate, and temperature. For patient with a baseline history of antihypertensive medications, blood pressure should be monitored at 3 hours ( $\pm 2$  hours) after the daily doses of anti-hypertensive medication.
7. Please refer to Section 6.3.2 for the assessments that should be completed as part of the Complete and Limited Physical Exams.

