17. **For subjects in Expansion Cohorts B, C, D, and E** - Survival follow-up (by telephone) should be performed every 12 ( $\pm$ 2) weeks from the date of the Treatment Completion visit. All subsequent anti-tumor therapy and information about ongoing or unresolved study drug-related SAEs will be collected. For the patients that discontinue the study without PD, all available tumor assessment results during survival follow-up will be recorded in the CRF until confirmation of PD. The date and cause of death should be recorded, if applicable. Patients who withdraw consent are encouraged to be followed for survival. If the patient has clearly expressed his/her refusal to be followed after withdrawal of consent, he/she will terminate the study and no survival follow-up will be performed.

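### Section 6.4 sends off-drug efficacy follow-up to Appendix A, but Appendix A schedules no imaging after the Treatment Completion visit, so the landmark PFS rate may lose patients who stop without progression

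*Protocol*

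**What the plan says.** Protocol Section 6.4 (Tumor Assessment) covers "Subjects who permanently discontinue study drug for reasons other than progression of disease" and says that they "should continue to be followed for efficacy according to the schedule in" Appendix A.

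In Appendix A, the row for dose escalation and Cohorts C, D and E reads "Screening, then every 8 (±1) weeks thereafter", with treatment-cycle labels (C3D1, C5D1, C7D1). The row for Cohorts A and B lists C2D1, C3D1 and C4D1 and then 8-week intervals, also by cycle. Both rows end with a mark at the Treatment Completion visit, 30 (±7) days after treatment is permanently stopped. Footnote 4 says "The treatment completion visit tumor assessment can be omitted if treatment ended because of disease progression", or if a scan was done within 14 days before the last dose.

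The Follow-up column is headed "Every 12 (±2) weeks from Treatment Completion Visit" and contains survival follow-up only. Footnote 17 opens "For subjects in Expansion Cohorts B, C, D, and E" and continues "Survival follow-up (by telephone) should be performed every 12" weeks. For patients who leave the study without progression it adds that "all available tumor assessment results during survival follow-up will be recorded in the CRF until confirmation of PD".

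SAP Appendix 1 repeats this schedule. In SAP Appendix 4 the on-treatment tumor windows end at the last dose, and one post-treatment window runs from last dose +8 to +37 days. Under SAP Section 16.1.5 (Table 1), a patient with neither progression nor death is censored at the last evaluable tumor assessment.

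**The concern.** Section 6.4 states an intention and leaves the timetable to Appendix A, and Appendix A supplies none. After the completion visit, whether progression is detected depends on scans obtained outside the trial schedule. For the dose-escalation patients and Cohort A, footnote 17 does not provide even for recording those.

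The primary endpoint of the expansion phase is the PFS rate, which Protocol Section 8.5 places at week 12 for Cohorts B and C and at week 16 for Cohorts D and E. Kaplan-Meier treats a censored patient as carrying the same future risk as those still being scanned. If patients who stop for toxicity progress faster once off drug, that assumption fails and the estimated rate is too high. The study is single-arm, so no comparator shares the same censoring, and the cohorts are small (40 or 15 patients). The SAP plans no sensitivity analysis for this kind of censoring.

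**Working it through.** **1. When can censoring fall before the landmark?** Cycles last 28 days, so C3D1 is day 57, C4D1 is day 85 and C5D1 is day 113. The landmarks are 12 × 7 = 84 and 16 × 7 = 112 days.

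Take a patient scanned at day 57 without progression who takes the last dose by day 57 + 14 = 71 and stops for toxicity. Footnote 4 allows the completion scan to be omitted. The scan at day 85 (Cohort B) or day 113 (Cohorts D and E) is tied to a treatment cycle that the patient no longer has. If the patient is alive and has no outside scan, PFS is censored at day 57, before either landmark.

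**2. What does the completion scan rescue?** It falls 23 to 37 days after the decision to stop.
- To reach day 84, the decision must come on or after day 84 − 37 = 47 at the earliest, or day 84 − 23 = 61 at the latest.
- To reach day 112, it must come on or after day 112 − 37 = 75 at the earliest, or day 112 − 23 = 89 at the latest.

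Where it is done, the completion scan therefore protects week 12 for stops from about week 8, but protects week 16 only for later stops.

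**3. The SAP's missed-scan rule.** The SAP gives 126 days for two consecutive assessments: 2 × (8 × 7 + 7) = 126, which reproduces. In a patient with any post-baseline scan, the gap to day 112 is under 126 days, so this rule cannot remove an event at the week 12 or week 16 landmark. It affects later events.

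**4. Cohort C at week 12.** Scheduled scans fall at weeks 8 and 16 whether or not the patient is on drug. Little scheduled information near week 12 is lost, so the effect there is smaller.

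**5. Size, by illustration only.** The documents give no rate of stopping without progression. Assumptions:
- PFS is exponential with median 3.71 months, the fruquintinib arm of the Phase 3 study described in Protocol Section 1.3.3.
- A share q is assigned a stop time uniform over weeks 0 to 12 and is censored at that time.
- The hazard after stopping is multiplied by m.

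Median: 3.71 × 30.4375 = 112.9 days. λ = ln 2 / 112.9 = 0.006138 per day. λT = 0.006138 × 84 = 0.5156.

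Kaplan-Meier rate with censoring at the stop: S = exp(−0.5156) = 59.7%.

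True 12-week rate among those assigned a stop time: s(m) = S × [1 − exp(−(m−1)λT)] / [(m−1)λT]. This gives 52.6% for m = 1.5, 46.7% for m = 2 and 37.3% for m = 3. For m = 1, s = S.

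True overall rate = (1 − q)S + q·s(m). Overstatement = q × (S − s(m)):

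| q | m = 1 | m = 1.5 | m = 2 | m = 3 |
|---|---|---|---|---|
| 10% | 0 | 0.7 points | 1.3 points | 2.2 points |
| 20% | 0 | 1.4 points | 2.6 points | 4.5 points |
| 30% | 0 | 2.1 points | 3.9 points | 6.7 points |

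A simulation of the same model agrees to within about 0.1 point. The table censors at the stop itself and so ignores the completion scan. Where that scan is done, the figures are smaller.

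**The case against.** Much of the case on the other side stands.

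- A reader might infer that PFS is censored because a patient stops for toxicity. Neither Protocol Section 8.5 nor SAP Table 1 says so. Censoring at the last scan follows only when no later scan, progression or death is recorded. Death without progression is an event, and survival follow-up collects deaths.
- A reader might infer that the two passages cannot both be obeyed. They can: a site may go on scanning under Section 6.4 and record the results under footnote 17. Section 6.4 also allows CT at any time when progression is suspected.
- A reader might infer from SAP Appendix 4 that a scan after day +37 would be discarded. Its windows serve visit-based summaries (SAP Section 5.4), whereas SAP Section 16.1.5 derives PFS from all assessments up to progression, death, withdrawal of consent or new therapy.
- A reader might suppose that every patient who stops has progressed by the landmark. With 10 to 20% stopping, a Kaplan-Meier rate of 50% would then become 0.9 × 50% = 45% or 0.8 × 50% = 40%. That is an outer bound. Nothing in the documents supports it as an estimate.
- The plan tests no hypothesis (SAP Section 5.5). Its stated precision is as wide as ±16 points for 40 patients and ±28 points for 15 (Protocol Section 8.6).
- Footnote 17 covers the cohorts to which landmark rates are assigned, so its silence on Cohort A and dose escalation matters little for the primary endpoint.

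One could also argue that the 8-week interval simply continues off drug. The cycle labels, the empty Follow-up cells and the SAP windows count against that reading. If it is what the sponsor means, the schedule should say so. The gap therefore remains: a site working from Appendix A orders no off-drug scan after the completion visit.

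**Conclusion.** The concern holds as an incomplete cross-reference with a consequence for the primary endpoint. Section 6.4 calls for efficacy follow-up after a stop without progression, and the schedule it cites plans no imaging beyond Treatment Completion. Some patients who stop early can be censored before week 12 or week 16, possibly informatively.

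The bias is upward only if those patients do worse than patients who stay on drug, which the documents neither show nor exclude. Under the stated assumptions (10 to 30% stopping, hazard ratio 1 to 3 after stopping, exponential PFS with a 3.71-month median) the 12-week overstatement runs from 0 to about 7 percentage points. That is inside the plan's own sampling uncertainty. Unlike sampling error, however, it would not shrink with more patients. The point is worth correcting, but it does not invalidate the design.

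**What to change.** Reconcile the passages.

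1. In the Follow-up column of Protocol Appendix A, show that tumor assessment continues at the cohort's existing interval for patients who stopped drug without progression, as Section 6.4 intends. The sponsor should state when that follow-up ends, because Section 6.4 does not.
2. Align footnote 17, which speaks of patients who leave the study, with Section 6.4, which speaks of patients who stop the drug. State which cohorts are covered.
3. Carry the change into SAP Appendix 1, and add tumor windows beyond last dose +37 days to SAP Appendix 4.
4. Where scans cannot be obtained, add a sensitivity analysis to SAP Section 16.2 that counts stops without progression before the landmark as events, and report the number of such patients per cohort. This gives a lower bound to set beside the main estimate.

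The cost is some off-drug scans that Section 6.4 already calls for but Appendix A does not yet schedule, an edit to one table and one footnote with the matching SAP text, and one extra analysis per cohort. Patients who start new anti-tumor therapy remain censored under SAP Table 1, so the scans reduce the problem without removing it entirely.
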